- Period 3 (Weeks 52 to 104): All subjects having clinical benefit per investigator and continuing on study treatment may proceed to Period 3 and receive 300 mg SC LY3074828 Q4W open-label starting at Week 52 through Week 104. Patients not receiving clinical benefit at Week 52 will discontinue treatment and will enter the Follow-Up period.
- Follow-Up (Weeks 104 to 120): At Week 104, subjects will stop treatment and be followed for safety for an additional 16 weeks.
- [Figure AMAG.1](#) illustrates the study design.

Abbreviations: IV = intravenous; Q4W = every 4 weeks; SC = subcutaneous; SES-CD = Simple Endoscopic Score for Crohn’s Disease.
 *Subjects who have not had any improvement in SES-CD score from baseline at Week 12, as determined by the central reader, will receive IV LY3074828 1000 mg + SC placebo.

Figure AMAG.1. Illustration of study design for Clinical Protocol I6T-MC-AMAG.

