Appendix 6. Additional Information on Systemic Drug Administration Reactions

Per investigator's judgement, in the absence of other plausible and more likely etiology, a systemic drug administration reaction is defined as the presence of any of the following symptoms (list is not exhaustive):

- Generalized urticaria or pruritus
- Angioedema at a location other than the injection site
- Throat tightness
- Difficulty swallowing/talking
- Stridor
- Chest tightness/dyspnea
- Wheeze/bronchospasm
- Hypoxemia
- Sense of impending doom
- Hypotension (systolic blood pressure change >20 mmHg from baseline)
- Syncope
- Cardiovascular collapse
- Vomiting
- Abdominal pain
- Diarrhea
- Bladder/bowel incontinence

**Appendix 7. Protocol Amendment I6T MC AMAG(b)
Summary: A Phase 2, Multicenter, Randomized,
Parallel-Arm, Placebo-Controlled Study of LY3074828 in
Subjects with Active Crohn's Disease (SERENITY)**

Overview

Protocol I6T-MC-AMAG (A Phase 2, Multicenter, Randomized, Parallel-Arm, Placebo-Controlled Study of LY3074828 in Subjects with Active Crohn's Disease [SERENITY]) has been amended. The new protocol is indicated by amendment (b) and will be used to conduct the study in place of any preceding version of the protocol.

The overall changes and rationale for the changes made to this protocol are as follows:

- Increased duration of all IV study drug administration to 2 hours. The 2-hour duration provides a rate (at the highest dose in Study AMAG) that approximates the rate being used across other mirikizumab studies.
- Addition of a 1-hour post infusion observation period to allow adequate evaluation of potential hypersensitivity or infusion related reactions.
- Added text on how to manage hypersensitivity events, including guidance on the collection of additional immunogenicity, PK, and hypersensitivity markers samples following a possible infusion related hypersensitivity event. Samples will be used to evaluate for possible etiologies of hypersensitivity reactions.
- Clarification added that patients who experience serious adverse reactions (anaphylaxis, systemic hypersensitivity event) related to an infusion are to have their investigational product discontinued.
- Clarification comments added to Schedule of Activities that additional immunogenicity, PK, and hypersensitivity markers samples may be collected in order to understand etiology of infusion related events

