LY+FUP	All LY3074828 (Lilly study drug) data for Periods 1-3 plus all Follow-Up combined
mBOCF	modified baseline observation carried forward
CCI	
MedDRA	Medical Dictionary for Regulatory Activities
CCI	
MMRM	mixed model for repeated measures
NAb	neutralizing antibody
Nab+	NAb positive

CCI	
NRI	non-responder imputation
NRS	numeric rating scale
OI	opportunistic infection
PD	pharmacodynamics
PGRC	Patient's Global Rating of Change
PGRS	Patient's Global Rating of Severity
PK	pharmacokinetics
PT	preferred term
PRO	patient-reported outcomes: a 2-item index comprised of the SF and AP items from the CDAI (unweighted)
PRO2	patient-reported outcomes-2: a 2-item index comprised of the SF and AP items from the CDAI (weighted)
Q4W	every 4 weeks
QIDS-SR16	Quick Inventory of Depressive Symptomatology–Self Report (16 Items)
REML	restricted maximum likelihood
RHI	Robarts Histopathology Index
SAE	serious adverse event
SAP	statistical analysis plan
SC	subcutaneous
SD	standard deviation
SES-CD	Simple Endoscopic Score for Crohn's Disease
SF	stool frequency
SF-36	36-Item Short Form Health Survey
SI	International System of Units
SMQ	standardized MedDRA query
SOC	system organ class
TE ADA-	treatment-emergent ADA negative

TE ADA+	treatment-emergent ADA positive
TEAE	treatment-emergent adverse event
ULN	upper limit of normal
US	United States

3. Revision History

SAP Version 1 was approved prior to the first permanent data transfer.

SAP Version 2 was approved prior to first unblinding. The overall changes and rationale for the changes incorporated in Version 2 are as follows:

- Reflected protocol amendment (a).
- Further defined subject populations, study periods, and baseline/postbaseline for analyses.
- Added exploratory endpoints not specified in protocol based on data from new publications.

4. Study Objectives

Table AMAG.4.1 shows the objectives and endpoints of the study as noted in the protocol. Further details on the endpoints, including derivations, are described in the corresponding section of this SAP.

Table AMAG.4.1. Objectives and Endpoints

Objectives	Endpoints
Primary	
To test the hypothesis that treatment with LY3074828 is superior to placebo in the proportion of subjects with endoscopic response at Week 12 , defined as 50% reduction from baseline in SES-CD	Proportion of subjects achieving endoscopic response at Week 12
Secondary	

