Period 1 (Weeks 0 to 12): A 12-week dosing period is designed to evaluate the efficacy and safety of LY3074828 administered intravenously at Weeks 0, 4, and 8. At baseline, subjects will be randomized with a 2:1:1:2 allocation across the 4 treatment arms (1000, 600, and 200 mg LY3074828, and placebo) and stratified on the basis of previous exposure to biologic therapy for treatment of CD.
- Period 2 (Weeks 12 to 52): Subjects will receive both IV and SC dosing to maintain blinding from Weeks 12 through 48.
 - All subjects who received LY3074828 treatment in Period 1 and who achieved an improvement in their Simple Endoscopic Score for Crohn's Disease (SES-CD) score from baseline at Week 12 (determined by the central reader) will be re-randomized evenly to either:
 - 1) continue Period 1 treatment assignment (IV LY3074828 1000 mg, 600 mg, or 200 mg every 4 weeks [Q4W]) with placebo administered subcutaneously.
 - 2) IV placebo Q4W with SC LY3074828 300 mg Q4W.
 - All subjects who received LY3074828 treatment in Period 1 and who did not achieve an improvement from baseline SES-CD score at Week 12 will receive IV LY3074828 1000 mg and SC placebo Q4W.
 - All subjects who received placebo in Period 1 will receive IV LY3074828 1000 mg and SC placebo Q4W.

Re-randomization will be stratified based on endoscopic response (i.e., achieving a 50% reduction in SES-CD score from baseline).

- Period 3 (Weeks 52 to 104): All subjects with clinical benefit and continuing on study treatment may proceed to Period 3 and receive SC 300 mg LY3074828 Q4W open label starting at Week 52 through Week 104. Clinical benefit is defined as having an endoscopic response (50% reduction from baseline in SES CD score), or a 25% reduction from baseline in SES CD score, combined with a 40% reduction from baseline in stool frequency (SF) or abdominal pain (AP) score. Subjects not receiving clinical benefit at Week 52 will discontinue treatment and will enter the Follow-Up period.

- Follow-Up Period (Weeks 104 to 120): At Week 104, subjects will stop treatment and be followed for safety for an additional 16 weeks. [Figure AMAG.5.1](#) illustrates the study design.

Abbreviations: ETV = early termination visit; IV = intravenous; Q4W = every 4 weeks; SC = subcutaneous; SES-CD = Simple Endoscopic Score for Crohn’s Disease.
 *Subjects who have not had any improvement in SES-CD score from baseline at Week 12, as determined by the central reader, will receive IV LY3074828 1000 mg + SC placebo.

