6.1.1. Subject Population for Analyses

Efficacy and safety analyses will be conducted on the populations defined in [Table AMAG.6.1](#).

Table AMAG.6.1. Subject Populations for Analyses

Population	Description
Efficacy and Health Outcomes (EHO)	
Intent-to-treat (ITT)	All randomized subjects at Period 1, even if the subject does not take the assigned treatment, does not receive the correct treatment, or otherwise does not follow the protocol. Subjects will be analyzed according to the treatment to which they were randomized. Note: Subjects who are screen failures and inadvertently randomized that did not receive study treatment will be excluded from the ITT population.
Modified Intent-to-Treat (mITT)	All randomized subjects at Period 1 who receive at least 1 dose of study treatment (regardless if the subject does not receive the correct treatment, or otherwise does not follow the protocol). Subjects will be analyzed according to the treatment to which they were randomized. Note: If deemed necessary, select endpoints (Endoscopic Response at Week 12, Endoscopic Remission at Week 12, PRO Remission at Week 12, and CDAI Total Score through Week 12) will be analyzed based on this population.
EHO Group 2	All subjects (including non-improvers and placebo subjects) entering Period 2. Subjects will be analyzed according to the treatment to which they were randomized in Period 2. Note: Subjects who discontinue treatment in Period 1 may continue in the study according to the visit schedule into Period 2. These subjects will be excluded from this population. If deemed necessary, the data for these subjects will be reviewed.
EHO Group 3	All subjects with clinical benefit at the end of Period 2 and continuing to Period 3.
Safety	
Safety Population Period 1	All randomized subjects at Period 1 who received at least 1 dose of study treatment during Period 1. Subjects will be analyzed according to the treatment to which they were randomized. This population is identical to the mITT population described above.
Safety Population Period 2	All subjects (including non-improvers and placebo subjects) entering Period 2 who received at least 1 dose of study treatment during Period 2. Subjects will be analyzed according to the treatment to which they were randomized in Period 2. Note: Subjects who discontinue treatment may continue in the study according to the visit schedule into Period 2. These subjects will not be dosed and therefore will not be part of this population.

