6.1.2. Study Period

Table AMAG.6.2 defines the study periods.

Table AMAG.6.2. Study Periods

Period	Start Date	End Date
Study Baseline	Informed Consent date	Prior to Visit 2 dose date/time. If dose date is missing, the last date at Visit 2 will be used.
Period 1 (Weeks 0-12)	After Study Baseline end date.	Prior to Visit 8 dose date/time or the date of the ETV (if it occurs between Visits 2 and 8). If dose date is missing, the last date at Visit 8 will be used.
Period 2 (Weeks 12-52)	After Period 1 end date.	Prior to Visit 18 dose date/time or the date of the ETV (if it occurs between Visits 8 and 18). If dose date is missing, the last date at Visit 18 will be used.
Period 3 (Weeks 52-104)	Only for subjects with Clinical Benefit: After Period 2 end date.	Visit 31 dose date or the date of the ETV (if it occurs between Visits 18 and 31). If dose date is missing, the last date at Visit 31 will be used.
Follow-up (Weeks 104-120)	
 • Subjects completed treatment and Period 3: After Period 3 end date. • Subjects discontinued treatment in Period 2 but completed Period 2: After Period 2 end date. • Subjects with no Clinical Benefit and did not enter Period 3: After Period 2 end date. • Subjects discontinued treatment in Period 3 but completed Period 3: After Period 3 end date. 	Visit 804 dose date or the date of the ETV (if it occurs between Visits 801 and 804), whichever is earliest.

Abbreviation: ETV = early termination visit.

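### The SAP ties EHO Group 3 and the Period 3 start date to a threshold definition of clinical benefit that the current protocol does not use, so some subjects treated in Period 3 may be left out of that group

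*SAP*

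**What the plan says.** **Protocol.** The synopsis and Section 5.1 carry the same entry rule: "All subjects having clinical benefit per investigator and continuing on study treatment may proceed to Period 3". Neither gives a numeric threshold. The overview in Appendix 7 states which version governs: "The new protocol is indicated by amendment (b) and will be used to conduct the study".

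**SAP.** The revision history says that Version 2 reflects protocol amendment (a). Section 5 defines the term: "Clinical benefit is defined as having an endoscopic response (50% reduction from baseline in SES CD score), or a 25% reduction" in SES-CD, "combined with a 40% reduction from baseline in stool frequency (SF) or abdominal pain (AP) score". The SAP contains no other definition. The term then appears in three working places:

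- Table AMAG.6.1, EHO Group 3: "All subjects with clinical benefit at the end of Period 2 and continuing to Period 3".
- Table AMAG.6.2, Period 3 start date: "Only for subjects with Clinical Benefit: After Period 2 end date".
- Table AMAG.6.2, one of the Follow-up start rows: "Subjects with no Clinical Benefit and did not enter Period 3: After Period 2 end date".

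The notes under the SAP study-design figure (Figure AMAG.5.1) also use it, to send subjects without clinical benefit at Week 52 to Visit 801.

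**The concern.** The two current documents describe different sets of subjects in Period 3. The protocol's set is whoever the investigator judges to benefit. The SAP's set is whoever meets a formula, and the formula defines an analysis population and a period boundary.

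Protocol Appendix 7 explains that investigator determination was adopted so that long-term efficacy could be assessed in a broad population. A threshold filter on EHO Group 3 can remove the very subjects whom that change admits. A display labelled as Period 3 efficacy would then not describe everyone treated in Period 3. Two programmers could also build different populations, one from the Section 5 formula and one from actual entry to Period 3.

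**Working it through.** The plan gives no figure to reproduce on this point. The check is a reading of the rules against each other.

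**Step 1. Who can be dosed in Period 3 yet fail the SAP rule.** The protocol can admit any of the subjects below on investigator judgement. The symptom columns refer to the larger of the SF and AP reductions.

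| SES-CD reduction | Symptom reduction under 40% | Symptom reduction 40% or more |
|---|---|---|
| Under 25% | fails | fails |
| 25% to under 50% | fails | meets |
| 50% or more | meets* | meets |

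*The punctuation in Section 5 also allows the symptom condition to be attached to both endoscopic branches. On that reading this cell fails too.

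**Step 2. What such a subject loses.**

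- Membership of EHO Group 3. Table AMAG.6.8 uses that group, alongside EHO Group 2, for PRO remission and response, PRO2 response and remission, PRO1 remission, and CDAI total score, remission and response, through Week 120.
- The Period 3 concomitant-medication summary (SAP 6.9), which is assigned to EHO Group 3 alone.
- A Period 3 start date in Table AMAG.6.2.

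**Step 3. What such a subject keeps.**

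- EHO Group 2, which requires entry to Period 2 and has no benefit condition. Table AMAG.6.5 gives it Periods 1, 2, 3 and follow-up, and Table AMAG.6.8 lists it for the same symptom endpoints through Week 120 where applicable.
- A Period 3 end date, which is not conditional on benefit, and the two Follow-up rows for subjects who completed Period 3 on or off treatment, which are not conditional either.
- The efficacy window. Table AMAG.6.3 runs it from the Period 1 start to the end of the period of interest, so the missing start date does not enter.
- Safety populations All SC LY and All LY, which are defined by dosing.
- Period 3 disposition (SAP 6.6) and protocol deviations (SAP 6.17), which are tabulated by EHO Group 2 or its treatment groups.

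**Step 4. Effect on an EHO Group 3 proportion.** Let *d* be the share of Period 3 entrants who miss the SAP rule, and let *a* and *b* be the remission rates in those who meet it and those who miss it. The SAP reports *a*. The treated group has (1 − *d*)*a* + *d*·*b*. The difference is *d*(*a* − *b*). The documents give none of the three values. Assumed values show the range:

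- *d* = 0: difference 0, whatever *a* and *b* are.
- *a* = 60%, *b* = 30%: the treated group has 0.9 × 0.60 + 0.1 × 0.30 = 57% at *d* = 10%, and 0.7 × 0.60 + 0.3 × 0.30 = 51% at *d* = 30%, against 60% reported.
- *a* = 30%, *b* = 60%: the treated group has 0.9 × 0.30 + 0.1 × 0.60 = 33% at *d* = 10%, and 0.7 × 0.30 + 0.3 × 0.60 = 39% at *d* = 30%, against 30% reported.

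The size depends on *d*, and the sign depends on whether *a* exceeds *b*.

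**The case against.** The strongest reply is that little turns on this. EHO Group 2 already summarises the same endpoints at the same visits without a benefit condition. Most period dates work, safety is defined by dosing, Table AMAG.6.5 plans no treatment comparison for EHO Group 3, and the stated response and remission objectives are at Weeks 12 and 52. All of that stands, and it sets the weight of the point.

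It does not remove the mismatch. EHO Group 2 has a different denominator: it includes subjects who never entered Period 3, and under SAP 6.3.1 those who stop treatment generally count as non-responders from then on. It is not a substitute for a summary of those treated in Period 3. The Period 3 concomitant-medication summary has no EHO Group 2 counterpart.

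It could also be said that clinical benefit in the SAP tables simply means the investigator's judgement. The SAP does not say so, and its only definition is the formula.

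A reader might infer two stronger things. One is that the affected subjects drop out of the analysis altogether; Step 3 shows that they do not. The other is that long-term maintenance would look better than it was. The filter does use SF and AP, which also enter the Period 3 outcomes, so upward bias is plausible. But the rule is mainly endoscopic and the Period 3 outcomes are symptom-based. A subject excluded for a small SES-CD change may have good symptom scores. The documents do not settle the direction.

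**Conclusion.** Wrong as written, with low impact. Followed literally, the SAP leaves out of EHO Group 3 any subject dosed in Period 3 on investigator judgement who misses the SES-CD, SF and AP thresholds, and gives that subject no Period 3 start. The EHO Group 3 displays and the Period 3 concomitant-medication summary would then not describe all subjects treated in Period 3.

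This is a conflict between current texts; the amendment history only explains how it arose. The conclusion assumes that the Section 5 definition governs the term wherever the SAP uses it. The number affected cannot be found from the documents and is zero if every admitted subject also meets the thresholds. Only descriptive summaries of open-label treatment are at issue. The primary analysis, its significance level and its power are unaffected.

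**What to change.** 1. In Table AMAG.6.1, define EHO Group 3 as all subjects who receive at least one Period 3 dose (Visit 18 onward). The protocol's Schedule of Activities already marks Week 52 dosing as the start of Period 3.
2. In Table AMAG.6.2, start Period 3 at that dose for everyone who receives it. Word the Follow-up row for subjects without benefit by absence of a Period 3 dose.
3. Reconcile the definition in SAP Section 5 and the notes under its study-design figure with the protocol synopsis and Section 5.1. Which entry rule applies is a clinical decision for the sponsor; items 1 and 2 work under either.

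The cost is a few lines of SAP wording and the matching population and period programming. No new data are needed.

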6.1. General Considerations

Statistical analysis of this study will be the responsibility of Eli Lilly and Company (Lilly) or its designee.

Continuous data will be summarized in terms of the number of observations, mean, standard deviation (SD), minimum, median, and maximum. Categorical data will be summarized in terms of the number of subjects in the analysis population, the number of subjects providing data at the relevant time point, frequency counts, and the percentages corresponding to the appropriate method. All confidence intervals (CIs) and statistical tests will be 2-sided unless otherwise specified.

All tests of the primary and secondary treatment effects, including health outcomes measurements will be conducted at a 2-sided alpha level of 0.10, unless otherwise stated.

The Schedule of Activities outlined in the protocol specifies the allowable windows for assessments. Assessments performed outside these windows are not expected to affect the primary outcomes and, as such, no subject /assessment will be excluded from any analysis due to this reason.

Data collected at early termination (ETV) visits will be entered under the visit in which it occurs. For by-visit summaries, only visits in which a measure was scheduled to be collected will be summarized.

Data summaries, analyses of results, and listings will be generated using SAS[®] Version 9.2 or later. Pharmacokinetic/pharmacodynamic (PK/PD) analyses will be carried out using other appropriate software. Not all displays described in this SAP will necessarily be included in the clinical study reports (CSRs). Not all displays will necessarily be created as a “static” display. Some may be incorporated into interactive display tools instead of or in addition to a static display. Any display described in this statistical analysis plan (SAP) and not provided will be available upon request.

Any change to the data analysis methods described in the protocol will require an amendment ONLY if it changes a principal feature of the protocol. Any other change to the data analysis methods described in the protocol, and the justification for making the change, will be described in the CSR. Additional exploratory analyses of the data will be conducted as deemed appropriate.

6.1.1. Subject Population for Analyses

Efficacy and safety analyses will be conducted on the populations defined in [Table AMAG.6.1](#).

Table AMAG.6.1. Subject Populations for Analyses

Population	Description
Efficacy and Health Outcomes (EHO)	
Intent-to-treat (ITT)	All randomized subjects at Period 1, even if the subject does not take the assigned treatment, does not receive the correct treatment, or otherwise does not follow the protocol. Subjects will be analyzed according to the treatment to which they were randomized. Note: Subjects who are screen failures and inadvertently randomized that did not receive study treatment will be excluded from the ITT population.
Modified Intent-to-Treat (mITT)	All randomized subjects at Period 1 who receive at least 1 dose of study treatment (regardless if the subject does not receive the correct treatment, or otherwise does not follow the protocol). Subjects will be analyzed according to the treatment to which they were randomized. Note: If deemed necessary, select endpoints (Endoscopic Response at Week 12, Endoscopic Remission at Week 12, PRO Remission at Week 12, and CDAI Total Score through Week 12) will be analyzed based on this population.
EHO Group 2	All subjects (including non-improvers and placebo subjects) entering Period 2. Subjects will be analyzed according to the treatment to which they were randomized in Period 2. Note: Subjects who discontinue treatment in Period 1 may continue in the study according to the visit schedule into Period 2. These subjects will be excluded from this population. If deemed necessary, the data for these subjects will be reviewed.
EHO Group 3	All subjects with clinical benefit at the end of Period 2 and continuing to Period 3.
Safety	
Safety Population Period 1	All randomized subjects at Period 1 who received at least 1 dose of study treatment during Period 1. Subjects will be analyzed according to the treatment to which they were randomized. This population is identical to the mITT population described above.
Safety Population Period 2	All subjects (including non-improvers and placebo subjects) entering Period 2 who received at least 1 dose of study treatment during Period 2. Subjects will be analyzed according to the treatment to which they were randomized in Period 2. Note: Subjects who discontinue treatment may continue in the study according to the visit schedule into Period 2. These subjects will not be dosed and therefore will not be part of this population.
Safety population All SC LY	All subjects who received at least 1 dose of LY3074828 SC treatment.
Safety Population All LY	All subjects who received at least 1 dose of LY3074828 treatment.

